9.2.2.3. Adverse Events of Special Interest

The following adverse events of special interest (AESIs) will be evaluated specifically to determine the safety and tolerability of ixekizumab over the range of doses selected for this clinical study.

AESIs for ixekizumab are:

- cytopenias (leukopenia, neutropenia, and thrombocytopenia),
- liver biochemical test changes/enzyme elevations (ALT, AST, bilirubin, and ALP),
- infections,
- immunogenicity,
- injection-site reactions,
- allergic reactions/hypersensitivities,
- cerebrocardiovascular events,
- malignancies,
- depression,
- inflammatory bowel disease, and

- interstitial lung disease.

If infections, injection-site reactions, or allergic/hypersensitivity reactions are reported, study sites will provide details on these events as instructed on the eCRF. Investigators will also educate participants and/or caregivers about the symptoms of allergic/hypersensitivity reactions and will provide instructions on dealing with these reactions. A blood sample will be collected when possible for any participant who experiences an AE of allergic reactions/hypersensitivities during the study.

In the case of suspected IBD, the participant should be referred to a gastroenterologist (preferably pediatric gastroenterologist) for evaluation and management. Data on suspected IBD, as identified by events possibly indicative of ulcerative colitis or Crohn's disease will be collected, and the events will be adjudicated by an external Clinical Events Committee (CEC) composed of gastroenterologists with expertise in IBD. The role of the CEC is to adjudicate defined clinical events in a consistent, and unbiased manner throughout a study. The importance of the CEC is to ensure that all events that have been reported are evaluated uniformly by a single group.

9.2.3. *Complaint Handling*

Lilly collects product complaints on investigational products and drug delivery systems used in clinical studies in order to ensure the safety of study participants, monitor quality, and to facilitate process and product improvements.

Participants will be instructed to contact the investigator as soon as possible if he or she has a complaint or problem with the investigational product so that the situation can be assessed.

9.3. *Treatment of Overdose*

For this study, any dose of ixekizumab greater than 80 mg within a 24-hour time period will be considered an overdose. Any dose of adalimumab greater than 40 mg within a 24-hour time period will be considered an overdose.

The sponsor does not recommend specific treatment for an overdose. In the event of an overdose, the investigator/treating physician should:

- Contact the medical monitor immediately
- For adalimumab patients, please reference the product label for additional information
- Evaluate the participant to determine, in consultation with the medical monitor, whether study intervention should be interrupted or whether the dose should be reduced
- Closely monitor the participant for any AE/SAE and laboratory abnormalities
- For ixekizumab participants only, obtain a plasma sample for PK analysis if requested by the medical monitor (determined on a case-

by-case basis)

- Document the quantity of the excess dose as well as the duration of the overdose in the CRF

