7.1. Treatments Administered

Study treatment is defined as any medicinal product(s) or medical device(s) intended to be administered to or used by a study participant according to the study protocol.

This study involves administration of ixekizumab by SC injection Q4W or adalimumab by SC injection Q2W. The ixekizumab and adalimumab doses in this study are based on weight ([Table RHCG.7.1](#)).

Table RHCG.7.1. Treatment Regimens

Regimen	Dose Week 0	Dose Open-Label Treatment Period (Week 2 to Week 14)	Dose Open-Label Extension Treatment Period (Week 16 to Week 104)	Dose Long Term Extension Treatment Period (Week 104 to Week 264)	Authorized as defined by EU Clinical Trial Regulation
Ixekizumab CCI [REDACTED]	CCI [REDACTED] SC injections)	CCI Q4W SC injection	CCI Q4W SC injection	CCI Q4W SC injection	Authorized and not used according to EU marketing authorization
Ixekizumab CCI [REDACTED]	CCI SC injection	CCI Q4W SC injection	CCI Q4W SC injection	CCI Q4W SC injection	Authorized and not used according to EU marketing authorization
Ixekizumab CCI [REDACTED]	CCI SC injection	CCI Q4W SC injection	CCI Q4W SC injection	CCI Q4W SC injection	Authorized and not used according to EU marketing authorization

Adalimumab CCI [REDACTED]	CCI SC injection	CCI Q2W SC injection	Responder^a: Adalimumab CCI Q2W SC injection Non-responders or participants opting to switch to ixekizumab^a: Appropriate dose according to weight Q4W (without a starting dose). Participants who are not switching to ixekizumab will undergo ETV at Visit 29 (Week 104).	All adalimumab participants will switch to ixekizumab. Appropriate dose according to weight Q4W (without a starting dose). Participants who are not switching to ixekizumab will undergo ETV at Visit 29 (Week 104).	Authorized and not used according to EU marketing authorization
Adalimumab CCI [REDACTED]	CCI SC injection	CCI Q2W SC injection	Responders^a: Adalimumab CCI Q2W SC injection Non-responders or participants opting to switch to ixekizumab^a: Appropriate dose according to weight Q4W (without a starting dose).	Adalimumab CCI [REDACTED]	Authorized and not used according to EU marketing authorization

Abbreviations: ACR 30 = 30% improvement in American College of Rheumatology criteria; JIA = juvenile idiopathic arthritis; OLE = open-label extension; OLT = open-label treatment; Q2W = every 2 weeks; Q4W = every 4 weeks; SC = subcutaneous.

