^a Participants receiving adalimumab during the OLT period who did NOT attain a JIA ACR 30 response at Week 16 will be switched to ixekizumab in the OLE period. Participants receiving adalimumab during the OLT period who did attain a JIA ACR 30 response at Week 16 will be given the option to switch or not to switch to ixekizumab in the OLE period. The decision to switch for participants who achieved a JIA ACR 30 response will be left to the participant/participant's caregiver and investigator. A switch from adalimumab to ixekizumab during the OLE period may also occur at any other visit after Week 16 based on the participant/patient's caregiver and investigator's decision.

Note: When switching from adalimumab to ixekizumab, the participant will not receive the ixekizumab starting dose, but will receive the appropriate ixekizumab dose per the participant's weight. The minimum required period between the last dose of adalimumab and first dose of ixekizumab is 2 weeks.

This study involves administration of ixekizumab and adalimumab (as a reference arm) by SC injection.

Ixekizumab doses will be prepared by study site personnel. All doses will be administered on site. The study drug should be at room temperature when injected. Possible injection sites include the abdomen, thigh, and upper arm (using the arm contralateral for blood samples for PK). The injection site should not be in a psoriatic lesion and should be rotated to another area for subsequent doses at the same visit as well as the next visit.

Dosing

The selected ixekizumab doses are:

- 1) CCI Q4W CCI
- 2) CCI Q4W CCI
- 3) CCI Q4W CCI

CCI

Post-Administration Observation

Participants should remain under observation for at least 1 hour after the first dose to monitor for safety. Following the first injection, and if no problems occur with that injection, participants will be observed for 30 minutes following injection at all other study visits.

CCI

Participants initiating treatment with ixekizumab at Week 0 (Visit 2) will receive the starting dose. The participants switching from adalimumab to ixekizumab during the study (starting at Week 16) will not receive the starting dose but will receive the appropriate regular dose according to their weight at each visit. Switching participants from the adalimumab to ixekizumab dosing treatment regimen should follow the post-administration observation guidelines.

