Participants requiring the starting dose of CCI of ixekizumab will receive CCI SC injections. Participants requiring the starting doses of CCI of ixekizumab will receive 1 SC injection, except for participants with a body weight of CCI who will receive the starting dose of 40 mg in CCI

These 2 injections will be separated by a minimum of 60 minutes. As per previous instructions in the protocol, the second CCI of ixekizumab will require a 30-minute observation period after the administration.

Participants requiring a lower dose of ixekizumab will have the dose prepared by CCI

CCI

The selected adalimumab doses are:

- 1) **CCI** Q2W for **CCI**
- 2) **CCI** Q2W for **CCI**

For training purposes, the proper procedures for the administration of the initial injection of adalimumab will be performed by clinical staff at Week 0 (Visit 2). Each participant or participant's caregiver must return to the clinical site for all injections and to be trained to inject adalimumab under the supervision of the investigator staff until the investigator judges the participant or participant's caregiver sufficiently competent to perform the injections independently. After this time, the participant or the participant's caregiver will be allowed to inject adalimumab at home.

The investigator or his/her designee is responsible for the following:

- explaining the correct use of the investigational agent(s) to the participant or participant's caregiver;
- verifying that instructions are followed properly;
- maintaining accurate records of investigational product dispensing and collection; and
- at the end of the study returning all unused medication to Lilly, or its designee, unless the sponsor and sites have agreed all unused medication is to be destroyed by the site, as allowed by local law.

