7.1.1. Packaging and Labelling

The study drug will be supplied by the sponsor in accordance with current good manufacturing practices (cGMP).

Ixekizumab will be supplied as an injectable solution in 1-mL, single-dose, prefilled, disposable manual syringes with study-specific labels. Each syringe of ixekizumab is designed to deliver ixekizumab 80 mg. Participants weighing >25 kg to <50.0 kg can opt for at-home administration when 40 mg prefilled syringe is available for the trial.

Adalimumab (originator or biosimilar) will be supplied by the sponsor or its designee in accordance with cGMP. Adalimumab will be supplied in 2 presentations to be administered based on participant's weight:

- 20 mg in a single-use prefilled syringe, or
- 40 mg in a single-use prefilled syringe.

Syringes will be supplied in cartons, with the appropriate quantity of syringes specific to the planned dispensing schedule of the study drug. Clinical study materials will be labeled according to the country's regulatory requirements. All study drugs will be

stored, inventoried, reconciled, and destroyed according to applicable regulations.

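### Protocol 9.3 sets one flat overdose limit per drug although dosing is by weight, so a doubled dose in a child due the smaller dose is not classed as an overdose

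*Protocol*

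**What the plan says.** Protocol Section 9.3 (Treatment of Overdose) gives one threshold per drug for every participant: "any dose of ixekizumab greater than 80 mg within a 24-hour time period will be considered an overdose" and "Any dose of adalimumab greater than 40 mg within a 24-hour time period will be considered an overdose". Neither sentence mentions weight or the dose due, and neither is redacted. An overdose starts a list of actions. The first is "Contact the medical monitor immediately". The others are a joint assessment of whether to interrupt or reduce treatment, close watch for adverse events and laboratory abnormalities, a PK sample for ixekizumab if the monitor asks for one, and a CRF record of the excess amount.

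Section 7.1 states that "The ixekizumab and adalimumab doses in this study are based on weight". The regimen table is largely redacted, but some amounts remain visible:

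- Section 7.1.1 supplies adalimumab in 20 mg and 40 mg prefilled syringes, chosen by weight.
- Section 7.1 describes a group of participants "who will receive the starting dose of 40 mg in" a manner that is blacked out.
- Section 7.1.1 foresees a 40 mg ixekizumab prefilled syringe for children above 25 kg and below 50 kg.

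On handling, "Each syringe of ixekizumab is designed to deliver ixekizumab 80 mg" (7.1.1) and "Ixekizumab doses will be prepared by study site personnel" (7.1). Section 7.1 adds: "Participants requiring a lower dose of ixekizumab will have the dose prepared by" a method that is redacted.

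**The concern.** In a trial that enrols children from 10.0 kg upward, an overdose limit should move with the dose due. Both flat limits instead equal a full unit of the larger presentation: one 80 mg ixekizumab syringe and one 40 mg adalimumab syringe. For ixekizumab this matters in practice, because a smaller dose has to be prepared from an 80 mg syringe. Forgetting to reduce it delivers exactly 80 mg, the largest amount that 9.3 does not flag. Doses are also re-set by weight during the extension periods (Section 7.4), so the chance of giving the wrong category's dose does not end at Week 0.

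What is at stake is the safety response after a dosing error in a lighter child, not any efficacy conclusion.

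**Working it through.** No sample size, power or error rate is involved. The check compares the dose given with the stated limit.

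**Inputs**

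- Ixekizumab limit: above 80 mg in 24 hours (9.3).
- Adalimumab limit: above 40 mg in 24 hours (9.3).
- Ixekizumab dose due in one group: 40 mg, explicit as a starting dose (7.1). A regular dose of 40 mg in the band above 25 kg and below 50 kg is an inference from the planned syringe (7.1.1).
- Adalimumab dose due in the lighter band: 20 mg (7.1.1).
- Lowest eligible weight: 10.0 kg (6.1).

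**Rule as written:** overdose if dose given > limit. Ratio to the dose due = dose given / dose due. The rule first applies only when this ratio exceeds limit / dose due.

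| Drug | Due | Given | Given / due | Above limit? | Limit / due |
|---|---|---|---|---|---|
| Ixekizumab | 40 mg | 80 mg | 80/40 = 2.0 | 80 > 80: no | 80/40 = 2.0 |
| Adalimumab | 20 mg | 40 mg | 40/20 = 2.0 | 40 > 40: no | 40/20 = 2.0 |

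In both cases an error of up to and including double the dose is outside the definition.

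**The 40 mg starting dose is probably split.** The text after it in 7.1 refers to two injections at least 60 minutes apart, so that dose is most naturally read as two injections.

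- Both injections doubled: 2 × 40 = 80 mg in total, not flagged.
- One full 80 mg syringe and the second injection withheld: 80 mg, not flagged.
- One full 80 mg syringe followed by the second injection: above 80 mg, flagged.

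So 9.3 catches one version of the error and misses the others.

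**Per kilogram.** The single ixekizumab limit equals 80/10 = 8.0 mg/kg at 10 kg and 80/50 = 1.6 mg/kg at 50 kg, a ratio of 8.0/1.6 = 5.0.

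**Other routes, set beside 9.3**

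- Section 7.6 has deviations from the regimen recorded in the CRF.
- Appendix 1 treats a wrong dose as a medication error, and Appendix 5 lists medication errors among events meeting the AE definition.
- Section 9.2.1 asks for AEs to be reported to the sponsor promptly, but only SAEs carry a 24-hour deadline.
- Appendix 5 obliges the investigator to arrange further tests when medically indicated or requested.
- Section 9.5 allows up to 3 extra PK samples by agreement.

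None of these requires the immediate monitor contact or the interruption review.

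**After the change.** With the limit set at the dose due, the thresholds become above 40 mg for the ixekizumab case and above 20 mg for the adalimumab case. Both doubled doses are then overdoses.

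**The case against.** The strongest reply is that the practical gap is narrow. A doubled dose would still be a recorded deviation and a medication error. The investigator must alert the sponsor to anything unusual (9.2), every on-site injection is followed by observation (7.1), extra tests and PK samples are available, and the PK sample in 9.3 is itself taken only on request. This stands as a limit on the consequence. What remains is immediate rather than merely prompt contact, the formal review of interruption or reduction, and close monitoring as a required step.

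The adalimumab error is also less likely than the ixekizumab one. Adalimumab comes in fixed-strength prefilled syringes, and cartons are assigned and confirmed through the IWRS (7.2). The documents give no error rate for either drug. A limit with no tolerance would also catch trivial excesses in hand-prepared partial doses. That is fair, and the fix allows for it.

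A reader might infer three stronger points that the documents do not support:

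- **The top Week 0 starting dose is itself an overdose under 9.3.** It is given as more than one injection, syringes hold 80 mg, and Section 5.4 implies that the starting dose is higher than the regular one. The amount is redacted, however. A 40 mg dose also appears to be split in two, so the number of injections does not show that a dose exceeds 80 mg. The 160 mg starting dose in Section 3.2 belongs to adult trials. This is a query to the sponsor, not a finding.
- **The lightest children could receive more than 2.0 times their dose unflagged.** That depends on regular doses that are redacted.
- **SAP 6.7 contains the same error because it counts injections.** SAP 6.7 is a compliance rule, and Protocol 10.3.2.4 leaves its further definition to the SAP. It is not a safety trigger, and counting injections there does not contradict 9.3.

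**Conclusion.** The point holds for the definition in Protocol 9.3 and for both drugs. As written, 80 mg of ixekizumab for 40 mg due and 40 mg of adalimumab for 20 mg due, each 2.0 times the dose, are not overdoses and do not trigger the section's required actions. The amounts used are visible in the documents: the 20 mg adalimumab presentation and the 40 mg ixekizumab starting dose. Only the extension to a regular 40 mg ixekizumab dose is inferred, from the planned 40 mg syringe. The consequence is a weaker required safety response in lighter children. Recording and error reporting remain in place, and no primary or secondary efficacy result changes. It should be corrected because the stated rule misclassifies a foreseeable error and the correction is small.

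**What to change.** Reword Section 9.3 for both drugs along these lines: *any dose above the protocol-specified dose for that participant's weight category at that visit (including the Week 0 starting dose where applicable) within 24 hours*. During the open-label treatment period the category is the one set by Week 0 weight, as Section 7.4 already provides. If wanted, add a small stated tolerance for partial doses prepared at the site.

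The cost is a short text change and a few more calls to the medical monitor. Section 9.3 already asks for the excess amount to be documented and Section 7.6 for deviations to be recorded, so this change should need little or no new data collection.

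Ask the sponsor to confirm whether the redacted top starting dose exceeds 80 mg. The wording above would settle that case either way.

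Aligning the over-dose criterion in SAP 6.7 with the new definition is optional. The administration log items listed in Protocol 7.6 do not include the milligrams given, so a dose-based compliance rule might need extra data capture.

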9.4. Safety

Any clinically significant findings from physical examination, vital signs measurements, or laboratory measurements that result in a diagnosis and that occur after the participant receives the first dose of investigational product should be reported to Lilly or its designee as an AE via eCRF. These events will also be considered as an AE if the event does not result in a diagnosis but is considered clinically significant by the investigator.

9.4.1. Physical Examination

The complete physical examination (excluding pelvic, rectal, and breast examinations) will be performed according to the Schedule of Activities (Section 2). This examination will determine whether the participant meets the criteria required to participate in the study and will also serve as a monitor for preexisting conditions and as a baseline for treatment-emergent adverse event (TEAE) assessment. All physical examinations throughout the study should include a symptom- directed physical evaluation as well as an examination of the heart, lungs, and abdomen and a visual examination of the skin.

9.4.2. Tanner Stage Scale

The Tanner Stage Scales are a series of line drawings that are designed to aid the participant or caregiver in appropriately assessing the sexual maturity of the participant at the time of the visit (Chavarro et al. 2017). Participants 8 years and older will be assessing their sexual maturity according to the Schedule of Activities (Section 2).

Once the participant reaches the score 5 in the scale, no further assessments are needed.

9.4.3. Vital Signs

For each participant, vital sign measurements should be conducted according to the Schedule of Activities (Section 2).

Any clinically significant findings from vital signs measurement that result in a diagnosis and that occur after the participant receives the first dose of study treatment should be reported to Lilly or its designee as an AE via electronic data entry.

9.4.4. Laboratory Tests

For each participant, laboratory tests detailed in [Appendix 2](#) should be conducted according to the Schedule of Activities (Section 2).

Blood volume restrictions are anticipated to be applicable for participants 2 to <8 years old and particularly for participants 10.0 to <20.0 kg in body weight; however, it may be used for older participants if local regulations require restrictions on blood volumes. The Blood Volume Prioritization Tool is provided in [Appendix 7](#).

Due to blood volume restrictions, some laboratory samples may not be collected (for example, cell flow cytometry in case needed to reduce blood volumes of a certain visit). Laboratory samples should be collected as described in a sponsor-provided weight-based prioritization chart.

Additional allowances to accommodate blood volume restrictions may include, but are not limited to the following:

- Blood draws for Visit 1 and Visit 2 may be divided over 2 days if the 24-hour blood volume limit is exceeded.
- Hepatitis B virus DNA will be collected as a reflex test prior to Visit 2 and is only required for participants who are positive for HBcAb.
- Hepatitis C virus RNA will be collected as a reflex test prior to Visit 2 and is only required for participants who are positive for HCV antibody.

Use of local anesthetics or devices consistent with local prescribing information is permitted during the study visit to ease discomfort associated with venipunctures. Lilly or its designee will provide the investigator with the results of laboratory tests analyzed by a central vendor, if a central vendor is used for the clinical study.

Any clinically significant findings from laboratory tests that result in a diagnosis and that occur after the participant receives the first dose of investigational product should be reported to Lilly or its designee as AE via electronic data entry.

The investigator must review the laboratory report, document this review, and record any clinically relevant changes occurring during the study in the AE section of the CRF. The laboratory reports must be filed with the source documents.

9.4.5. *Pregnancy Testing*

See the Schedule of Activities (Section 2) for frequency of pregnancy testing and [Appendix 2](#) and [Appendix 6](#) for additional details about these tests. As per Clinical Trial Facilitation Group (CTFG) recommendation: In each case of delayed menstrual period (over 1 month between menstruations), confirmation of absence of pregnancy is strongly recommended. This recommendation also applies to women of childbearing potential (WOCBP) with infrequent or irregular menstrual cycles.

At Screening

Serum pregnancy tests will be given prior to the first dose of the study intervention for females ≥ 10 years of age (<10 years at investigator discretion) if menarche has been reached or if there is reason to believe the participant is sexually active. Pregnancy test results at screening must be known prior to first dose of the study intervention.

Open-Label Treatment, Open-Label Extension Treatment, and Long-Term Extension Periods

Female participants of childbearing potential (age 10 and older if menarche has been

reached or if there is reason to believe the participant is sexually active, or younger participants per investigator assessment of sexual maturity) will undergo a urine pregnancy test at the clinic on a monthly basis during scheduled visits through Week 264 or the ETV. Additional urine pregnancy testing may be performed at the investigator's discretion. Participants determined to be pregnant will be discontinued from treatment and will no longer be administered study intervention (see Section 8.1.1).

During the Post-Treatment Follow-Up Period

As indicated in the Schedule of Activities, urine pregnancy tests will be collected during each of the post-treatment follow-up visits.

